7.6 Safety pharmacology

A number of safety pharmacology end-points concerning the central nervous system (CNS), cardiovascular system, respiratory system, gastrointestinal system, renal/urinary system, and hematopoietic system, have been integrated into standard toxicity studies of AFM13 in cynomolgus monkeys. No alerts with regard to safety pharmacology arose from these studies that might call for additional in-depth investigations of AFM13.

7.6.1 Tissue cross-reactivity

In human non-epithelial tissues the staining pattern shown by AFM13 is consistent with its specificity, detecting only CD16- and CD30-positive cells. However, AFM13 shows strong immunostaining of a number of secretory-type human epithelia, including those of breast ducts, pancreatic ducts, acinar cells of the prostate, sweat glands of skin, and glandular epithelium of the uterine cervix. Furthermore, AFM13 shows staining of some non-secretory epithelia, including those of the urinary bladder, the fallopian tube, the ureter, and epididymal epithelial cells in the testis. The relevance of these findings is unclear. However, the same pattern of epithelial binding has been observed in cynomolgus monkeys without adverse toxicity.

Overall, AFM13 has a low toxic potential but potentially adverse hematological effects have to be taken into account.

7.7 Phase I clinical trial in relapsed or refractory Hodgkin lymphoma

A clinical phase I study, AFM13-101, was conducted in patients with heavily pre-treated relapsed/refractory HL [29]. The trial results are summarized in the sections below.

7.7.1.3 Efficacy analyses of the AFM13-101 trial

All 28 patients had measurable levels of sCD30 at the start of cycle 1 and in 24 patients the sCD30 level was decreased at the end of the first cycle. All patients treated in the dose cohorts of 1.5 mg/kg AFM13 experienced a marked decrease of sCD30. Furthermore, immunophenotypic analyses showed that AFM13 resulted in an increase of activated NK cells in the peripheral blood as measured by CD69 expression on their surface.

[figure not shown]
Of the 26 patients who were eligible for efficacy assessment, 3 patients achieved a partial response (PR), and 13 patients experienced a stable disease (SD) as documented at the final study visit. More detailed efficacy analyses indicate that the clinical activity is more pronounced at or above a dose of 1.5 mg/kg. Of the 13 patients treated at or above a dose level of 1.5 mg/kg, 7 patients experienced a SD and only 3 patients developed a progressive disease (PD) at the end of the trial. Two of the reported PRs were documented at a dose level of 1.5 mg/kg and one PR at the dose level of 4.5 mg/kg given twice a week. A waterfall plot analysis showed a reduction of the tumor volume in 8 patients treated at a dose level of 1.5 mg/kg or above [29, 34].

7.7.1.4 Pharmacokinetic analyses of the AFM13-101 trial

Pharmacokinetic analyses revealed that weekly dosing is suboptimal because the documented half-life of AFM13 was between 9 - 19 h in the dose cohorts \geq 1.5 mg/kg and because the serum levels in the weekly dose schedule were mostly below the serum level of 400 ng/ml which was defined as trough blood level as a result of *in vitro* data. Also, the bi-weekly regimen did not result in adequate trough levels at the end of the infusion intervals.

Furthermore, the measurement of NK cell activation with immunophenotypic analysis of CD69+ cells in the peripheral blood showed a correlation between the biological activity of AFM13 and its PK (Figure 2).

Figure 2: Correlation between NK Cell Activation and PK of AFM13

Thus, these PK data indicate that the dosing has to be done more frequently than bi-weekly at least for some defined period of time.

7.8 Rationale

Natural killer cells play an important role in tumor immune-surveillance [8, 10, 30]. Their function is regulated by a repertoire of inhibitory and activating surface receptors. NK cell-mediated cytotoxicity can occur through distinct mechanisms: (1) by activating the receptor NKG2D and NCR, and (2) through the potent activating receptor CD16 (Fc γ RIII) which mediates ADCC [8]. Enhanced expression of NK cell antigens has been shown to correlate with systemic anti-tumor response in early primary CTCL [31]. Further, phase I clinical data with AFM13 indicate that engagement of NK cells results in pharmacodynamic and clinical activity in relapsed/refractory HL. However, NK cell migration into the tumor, cytokine release in the tumor, potential effects on the adaptive immune response and other biological processes triggered by NK cell activation have not been investigated and are not understood so far.

Thus, we hypothesize that if we are able to engage the innate immune system through a specific activation and recruitment of NK cells via CD16A to tumors expressing CD30, then we intend to demonstrate an immunological and/or tumor response that might be broadly described in relation to dosing/PK parameters and could serve as a good and useful parameter in predicting clinical response.

The therapeutic potential of manipulating NK cell function via CD16 for the treatment of cancer has been previously demonstrated through the use of mAbs [32]. Presently, novel single chain fragment variable (scFv) recombinant reagents (BiKE and TriKE), which specifically target CD16 expressed on effector NK cells and antigens-of-interest on tumor cells, are being developed and tested for clinical use [33]. Further, a novel tetravalent bispecific CD30/CD16A antibody, AFM13, was investigated in a phase I study in HL patients and was demonstrated to be safe and active [29, 34]. We plan to investigate AFM13 and evaluate its ability to facilitate and redirect the NK cells in eliminating CD30-positive lymphoma targets in the skin and, by inference, other organs involved by the lymphoma.

Primary cutaneous CD30-positive lymphoproliferative LPD represent a spectrum from LyP, to primary cutaneous anaplastic large cell lymphoma (C-ALCL), to transformed mycosis fungoides (TMF). The most indolent form of primary cutaneous CD30-positive LPD is LyP, which is usually well controlled with low dose oral methotrexate, but control of the disease frequently requires life-long therapy. In contrast, TMF is an aggressive disease which does not have a standard of care, as patients are treated with various modalities of care with variable outcomes [20]). The spectrum of other CD30-positive lymphomas with cutaneous presentation is very broad and involves systemic B and T cell lymphomas with various clinical behaviors. Again, redirecting NK cells towards these CD30-positive malignancies through direct engagement with AFM13 is expected to induce tumor cell killing through NK cell-mediated and T cell-mediated cytotoxicity (i.e., cytotoxic T lymphocytes [CTL]).

8 STUDY OBJECTIVES

8.1 Primary Objectives

The primary objectives of this study are to:

1. Determine the intratumoral NK-cell and T-cell infiltrate and density
2. Determine the immunophenotype of immune cells (NK cells, T cells and others) in tumor and peripheral blood
3. Quantitate the plasma cytokine production and release in tumor and peripheral blood as a function of treatment.

8.2 Secondary Objectives

Secondary objectives are to:

1. Evaluate the safety and toxicity of AFM13
2. Determine the clinical efficacy, namely objective response rate (ORR), [including complete response (CR) and partial response (PR)], duration of response (DOR) and progression-free survival (PFS) as defined in the Revised Response Criteria for Malignant Lymphoma 2007 and modified Severity-Weighted Assessment Tool (mSWAT)
3. Evaluate the pharmacokinetic profile (PK) of AFM13.

8.3 Exploratory Objectives

Exploratory objectives are to:

1. Determine the immunogenicity of AFM13
2. Detect and quantify circulating tumor cells (CTC).

9 INVESTIGATIONAL PLAN

9.1 Overall Study Design and Plan

9.1 Description

This is an open label, Phase Ib/IIa study designed to evaluate the biologic activity of AFM13 in patients with relapsed or refractory CD30-positive lymphomas with cutaneous involvement.

The primary objective of this trial is to study the biologic and immunologic effects induced by the administration of various doses of AFM13, when given as a single agent. The study will enroll at least 9 patients with CD30-positive cutaneous lymphoma. Patients will be assigned to 3 dose cohorts of 3 patients each. As this is not a dose-finding study, there are no stringent criteria for initiation of subsequent cohorts: subsequent cohorts will be progressively enrolled after all 3 patients from the previous dose cohort have received their first planned treatment dose(s) during the first week of the cycle, and the safety of the patients on Week 2 Day 1 of the first cycle is deemed acceptable by involved investigators (Table 1).

After preliminary analysis of Cohorts 1-3, input from a scientific advisory board and the companies own experience in the Hodgkin's Study of AFM-13, it was decided to investigate an intermediate dose of 4.5mg/kg. Studying the intermediate dose may optimize some of the efficacy seen in Cohort 1 while reducing steroid use seen in Cohort 2 to manage infusion related reactions. An additional 3 patients will be recruited into Cohort 4. Afterwards a three patient expansion will be planned to confirm efficacy and tolerability of the selected cohort for a phase 2 study.

Table 1: Treatment Cohorts and Dosing Schedule (one cycle of treatment)

Cohort	Dose regimen			Total exposure
	Dose	Timing	Period	
Cohort 1	1.5 mg/kg	weekly	weeks 1-8	12 mg/Kg
Cohort 2	7.0 mg/kg	weekly	weeks 1-8	56 mg/Kg
Cohort 3	7.0 mg/kg (1 mg/kg applied as loading dose and 6mg/kg as continuous infusion for 5 days per week)	weekly	weeks 1-8	56 mg/Kg
Cohort 4	200mg	weekly	weeks 1-8	1600mg

Prior to recruitment into this trial, all patients will be assessed individually to document eligibility into the trial according to the Inclusion and Exclusion Criteria. Additionally, documentation of patient briefing and signed informed consent form (ICF) are mandatory requirements for trial participation. The protocol mandates that the primary diagnosis of CD30-

positive lymphoma be confirmed by the Department of Pathology at Columbia University Medical Center (CUMC). Patients whose diagnosis was made at a different institution will consent to have their biopsy material forwarded to CUMC for confirmation. CD30 expression will be confirmed using the BerH2 antibody. To date, there is a suggestion that the level of CD30 may not be important in predicting response; it is unclear what the lower limit should be. The data from Kim et al. [37] suggest that patients with <5% positivity for CD30 respond less well than patient who have more than 5%. Although this is the first paper to suggest a relationship on a lower level of expression and response..

Each patient eligible for the study will be asked to give consent for the collection of fresh tumor material. The completion of all staging assessments is also mandatory before registration into this trial. The patient will receive one 8-week cycle of protocol treatment followed by 3 weeks off and will be assessed for treatment/tumor response thereafter at week 11. All patients who achieve at least SD will receive a second cycle of protocol treatment at the same dose administered during Cycle 1, starting in what would be considered Week 12. During treatment and follow-up, patients will be closely monitored for safety. The biological and immunological effects of the treatment will be assessed in Cycle 1 only. A schematic overview of treatment, interventions and assessments (safety, feasibility, and efficacy) is given in Table 2.

In cohort 1 and 2 AFM13 will be administered in all patients as a slow intravenous (IV) infusion over 4 hours. The duration of the infusions will be stepwise shortened by 30 minutes to a minimum infusion rate of 1 hour if well tolerated by the patient. In cohort 3 weekly treatment will consists of a loading AFM13 dose of 1 mg/kg to be applied on day1 as 1-hour infusion, followed by a 6 mg/kg AFM13 as continuous infusion over 5 days. For further specifications please refer to the pharmacy manual. Cohort 4 will use the same dosing schedule as cohorts 1 and 2.

The biological and immunological studies will investigate the NK cell phenotypic characteristics, proliferative response (Ki-67), activation status (CD69), and density in the peripheral blood. The same analyses will be conducted in the tumor tissue collected from all patients at different time points. In addition, tumor cell infiltrate by NK cell and their spatial distribution in the tumor and its microenvironment will be studied. NK effector function will be assessed in both compartments (peripheral blood and tumor) by assaying for ADCC, presence of cytolytic proteins (granzyme B, perforin-1), and the production and release of cytokines and chemokines. T cells phenotype and effector function (CTL) will also be studied. Additionally, tumors obtained from study participants will be analyzed for expression of CD30, major histocompatibility antigens (MHC Class-I), other immune cell infiltrates, and resident immune cells (myeloid-derived suppressor cells, regulatory T cells (Tregs).

The presence of anti-AFM13 antibody will be investigated, and their neutralizing ability assayed.

Continuous safety analyses (AEs, safety clinical laboratory assessments, vital signs, ECGs) will be regularly performed by a Principal Investigator-led safety team to ensure the safety of

the patients. In the case of a potential significant safety problem the Principal Investigator in consultation with groups such as the FDA, IRB, data monitoring committee and/or statisticians may decide on the termination or temporary cessation of the trial.

9.2 Dose Rationale

Different doses and dose regimens are investigated in this translational research study aiming to understand the impact of the dose regimen on the biological and immunological effects of AFM13 in the tumor. The selected dose regimens of the 3 cohorts are based on the target dose and dose regimen of AFM13 being investigated in a Phase II proof-of-concept study in relapsed/refractory HL. In the Phase II study, 2 dose regimens are investigated which are identical to dose Cohorts 1 and 2 of this study. A third cohort of continuous intravenous infusion was added which is identical to Cohort 3 of the HL study. A fourth cohort, of an intermediate dose between Cohort 1 and 2 was also added.

The rationale for the selection of dose and dose regimen in Phase II is based on data from the phase I trial including a PK modeling as well as pre-clinical cytotoxicity data.

In the phase I study, it was shown that pharmacodynamics and clinical effects are more pronounced at AFM13 doses ≥ 1.5 mg/kg without having a negative effect on the safety profile. It was therefore concluded that the dose in future studies should be at least 1.5 mg/kg (Cohort 1 of the current study).

Phase I PK data have been collected and analyzed after weekly doses of AFM13. Data revealed that a defined minimum trough plasma level of AFM13 could not be maintained with weekly infusions (Refer to Figure 1). This minimum plasma level of 400 ng/mL, indicated by the dotted line in Figure 2, was calculated based on the EC₅₀ of *in vitro* cytotoxicity assays and considering physiological conditions like the presence of IgG in blood as well as the barrier from the vascular compartment to the HL lesion.

In parallel to the AFM13 plasma levels, the portion of activated NK cells (relative to the total number of NK cells) increased after AFM13 infusion but dropped during the weekly infusion period back to baseline prior to the next infusion. This finding supports that more frequent dosing is needed at least in the initial phase of treatment. PK modeling revealed that 1.5 mg/kg AFM13 administered 3x per week succeeds in maintaining AFM13 plasma levels above 400 ng/mL (Figure 2). Therefore, this dose regimen was defined for the initial 2-week treatment phase with AFM13.

Considering clinical feasibility aspects, it was decided for the Phase II study that, after the initial treatment phase, AFM13 will be dosed 7 mg/kg weekly (Cohort 2 of the current study). The dose regimen of 1.5 mg/kg 3x per week over 2 weeks followed by 7 mg/kg weekly over 6 weeks (Figure 3) is currently in Phase II clinical development. AFM13 is administered in 8-week cycles.

PK modelling based on the data gathered from the phase I study and as well from the currently ongoing phase II study revealed that a more stable serum levels of AFM13 can be achieved

with continuous infusion (CIVI) of 6mg/kg over 5 days after a loading dose of 1 mg/kg. Therefore, a new cohort is currently being investigated with the German Hodgkin Study Group to assess efficacy of a CIVI dosing scheme identical as planned in this study. (Cohort 3 of the current study)

Figure 1: PK profile for 1.5 mg/kg AFM13 administered weekly

[figure not shown]

Figure 2: Simulated PK profile for 1.5 mg/kg AFM13 administered three times per week

[figure not shown]

Figure 3: Simulated PK profile for 1.5 mg/kg AFM13 administered weekly over 2 weeks followed by 7 mg/kg weekly over 6 weeks

[figure not shown]
[figure not shown]

Figure 4: Simulated PK profile for 7.0 mg/kg AFM13 administered weekly by continuous infusion

For Cohort 4: The rationale for the selected dose and schedule of 200 mg is based on an updated analysis of the overall pre-clinical and clinical experience from the completed AFM13-101 Phase I study and the other ongoing AFM13 clinical studies (including present study). An exposure-response analysis was completed based on the data from the AFM13-101 Phase I study.

The PK data from the AFM13-101 showed that overall, the systemic exposure to AFM13 increased in a slightly greater than dose proportional fashion (an increase of 2.14 and 2.30-fold for C_{max} and $AUC_{0-\infty}$, respectively), the systemic exposure increase from the dose 1.5 mg/kg to 7 mg/kg (4.7-fold), geometric mean C_{max} and $AUC_{0-\infty}$ increased 9.6-fold and 13.2-fold, respectively i.e. approximately 2- to 3-fold greater than expected based on a proportional relationship.

Exposure-response analyses for the study showed that achieving an $AUC_{0-\infty}$ of at least 100,000 h*ng/mL appears to be important to increase the likelihood of achieving clinical benefit and the proposed stratified flat dose of 200 mg corresponded to a dose of

approximately 3 mg/kg; which is also significantly lower than the dose of 7 mg/kg, a dose level that was associated with increased incidence and severity of AFM13-associated IRRs.

Completed population PK analysis using data from AFM13-101 and the current study, there were three variables that had a statistically significant impact on PK parameters as listed below:

- Dose: higher doses had a greater effect on the central volume of distribution (i.e. with higher doses, more of the drug stays within the central compartment)
- Body surface area (BSA): higher BSA had proportionately lower C_{max} ; however, BSA had no significant impact on the AUC
- Albumin: lower albumin led to faster clearance, thereby impacting the AUC.

While these results do not alter the proposed dose selection of 200 mg, an interim PK analysis using further PK data from patients treated in this study will be utilized to determine if the above described effect on albumin is confirmed and to determine if a higher dose of AFM13 is warranted for patients with very low albumin.

9.3 Number of Centers

This study will be conducted at CUMC in the United States of America (USA).

9.4 Number of Subjects

The study will enroll 15 evaluable subjects. Evaluable patients are defined as having 1 biopsy pre-treatment and at least 1 biopsy post treatment.

9.5 Schedule of Assessments

See Table 2 for Schedule of Assessments. The details for blood draw per assay are given in the Immunobiology Research Manual.

Table 2: Schedule of Assessments

Week	Screening	1	2	3	4	5	6	7	8	11	EoS/PD ^p
Day	-28 to 0	1	5	1	1	1	1	1	1	1	1§
AFM13 Administration ^a	Cohort 1		x	x	x	x	x	x	x		
	Cohort 2		x	x	x	x	x	x	x		
	Cohort 3		x	x	x	x	x	x	x		
	Cohort 4		x	x	x	x	x	x	x		
Informed consent	x										
Eligibility	x										
Demographics	x										
Medical/surgical history	x										
ECOG performance status	x										
Pregnancy test ^b	x										
Histology CD30+ lymphoma ^c	x										
Physical examination ^d	x	x	x	x	x	x	x	x	x	x	x
ECG (rest 12-lead) ^e	x		x		x		x		x		x
Vital signs ^f	x	x	x	x	x	x	x	x	x	x	x
Clinical chemistry	x	x	x	x	x	x	x	x	x	x	x
Hematology	x	x	x	x	x	x	x	x	x	x	x
Coagulation	x				x				x		x
Urinalysis	x				x				x		x
Trough serum levels ^{g,j*}		x		x	x	x	x	x	x		
Full AFM13 PK sampling ^{h,j}		x ^h				x ^h					
Skin biopsy ⁱ		x	x		x			x		x ⁿ	
Blood immunology		x	x		x			x		x	x
Blood cytokines ^{j,k}		x	x		x			x		x	x
sCD30 ^j		x	x		x			x		x	x
ADAs ^j		x		x						x	
Tumor assessment ^o : (m)SWAT ^m		x								x	
		x								x	
		x								x	
Flow Cytometry		x								x	
¹⁸ FDG-PET and CT-Scans ^l		x								x	
Concomitant medication	x	x	x	x	x	x	x	x	x	x	x
Adverse event	x	x	x	x	x	x	x	x	x	x	x

Optional 8 Week Schedule

Week	1	2	3	4	5	6	7	8	11	EoS/PD ^p
Day	1	1	1	1	1	1	1	1	1§	
AFM13 Administration ^a	Cohort 1	x	x	x	x	x	x	x		
	Cohort 2	x	x	x	x	x	x	x		
	Cohort 3	x	x	x	x	x	x	x		
	Cohort 4	x	x	x	x	x	x	x		
Physical examination ^c	x	x	x	x	x	x	x	x	x	x
ECG (rest 12-lead) ^d	x	x		x		x		x		x
Vital signs ^e	x	x	x	x	x	x	x	x	x	x
Clinical chemistry	x	x	x	x	x	x	x	x	x	x
Hematology	x	x	x	x	x	x	x	x	x	x
Coagulation	x			x					x	x
Tumor assessment ^o :										x
¹⁸ FDG-PET and CT-Scans ^l										x
(m)SWAT ^m										x
Flow Cytometry										x
Concomitant medication	x	x	x	x	x	x	x	x	x	x
Adverse event	x	x	x	x	x	x	x	x	x	x

ADA=anti-drug antibody; CT=computerized tomography; CTC=circulating tumor cells; ECOG=Eastern Cooperative Oncology Group; ECG=electrocardiogram; EoS=end of study; ¹⁸FDG-PET=fluorodeoxyglucose-positron emission tomography; MRI=magnetic resonance imaging; m(SWAT)=modified Severity-Weighted Assessment Tool; PD= progression of disease. PK=pharmacokinetics; SD=stable disease;

Additional assessments may be conducted as clinically indicated

Assessments made on drug administration days are to be conducted prior to the start of study medication infusion, unless specified otherwise

Patients with clinical benefit (SD, PR, CR) will receive a second cycle starting after week 11.

All study procedures have a +/- 3 day window, unless otherwise specified.

§ Restaging is to be done at each Week 11 Visit +/- 2 weeks.

- a. AFM13 is infused over 4 hours at the first infusion day. Infusion duration is to be stepwise reduced by 30 min to a minimum of 1 hour at the following infusion days. Cave: measures related to infusion duration in case of adverse events. In cohort 3 weekly treatment will consist of a loading AFM13 dose of 1 mg/kg to be applied on day 1 as 1-hour infusion, followed by a 6 mg/kg AFM13 as continuous infusion over 5 days.
- b. Pregnancy test done at screening must be within 7 days of treatment initiation.
- c. A histological confirmation of CD30-positive lymphoma can be made using the previous tumor biopsy (paraffin-embedded tissue block and slides).
- d. Physical examination will include recording the patient's weight and height at Screening and weight at the End of Study visit. Symptom-directed physical examinations at other time points are to be done as needed.
- e. Additional ECGs will be obtained if clinically indicated. All ECGs will be done on local equipment.
- f. Vital signs include temperature, systolic blood pressure, diastolic blood pressure, heart rate and respiratory rate.
- g. Collected prior to all infusions, during Cycle 1 only
- h. Blood samples for full PK to be taken for cohort 1, 2 and 4 prior to infusion and at the following times points after end of first infusion on Week 1 Day 1 and Week 5 Day 1 only: 0, 2, 4, and 24 +/- 4 hours, for cohort 3: prior to infusion and at the following time points after end of the loading dose on Week 1 Day 1 and Week 5 Day 1 only: 0, 2, 4, and 24 +/- 4 hours
- i. Skin biopsies on Day 1, pre-treatment (can be taken -7 days from day 1) and 5 (can be taken -1 day from day 5 or up to +3 days) should be taken from different lesions, if possible. If this is not possible, the biopsy on Day 5 should be taken from as far away as possible from the first one (at least 3 cm).
- j. Blood needs to be centrifuged and serum to be frozen.
- k. Blood for cytokines has to be taken prior to infusion, at the end of infusion and 2 hours after end of infusion on Week 1 Day 1, Week 4 Day 1 and Week 8 Day 1. Optional sample will be collected upon PD or EoS.
- l. ¹⁸FDG-PET and CT-Scans carried out within 4 weeks prior to the first dose.
- m. Skin examination with photo-documentation (part of SOC); evaluation using mSWAT Tool
- n. Optional biopsy investigator discretion
- o. All assessments will be performed at screening, only positive assessment needs to be followed for response
- p. Follow up guidelines per section 10.11

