9.6.2 Screening Period (Day -28 to Day 0)

Subjects are to undergo a screening visit ≤ 28 days prior to the planned first day of study treatment. Prior to conducting any Screening activities that are not considered standard of care, the investigator or designee is responsible for obtaining signed and dated written ICF and HIPAA authorization from the patient (Sections 9.6.1& 10).

Screening assessments are as follows:

- Check eligibility against study Inclusion and Exclusion Criteria (Sections 10.11.1 and 0, respectively)
- Record demographic information (age, race, gender, ethnicity)
- Record medical and surgical history
- Assess ECOG performance status
- Perform a pregnancy test on women of childbearing potential; negative results must be confirmed within 7 days prior to administration of first treatment (pregnancy testing must use same test format for all patients)
- Histological confirmation of CD30-positive lymphoma
- Physical examination (including weight and height)
- 12-lead ECG
- Vital signs (temperature, systolic blood pressure, diastolic blood pressure, respiratory rate)
- Clinical laboratory tests (chemistry, hematology, coagulation and urinalysis)
- Tumor assessment (fluorodeoxyglucose-positron emission tomography [$^{18}\text{FDG-PET}$] and computerized tomography (CT) scans not older than 4 weeks prior to the first dose can be used as baseline).
- mSWAT skin examination with photo-documentation (part of SOC)
- Documentation of concomitant medications and AEs.

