10.11 Selection of Study Population

10.11.1 Inclusion Criteria

Both men and women of all races and ethnic groups are eligible for this trial.

Patients eligible for enrolment in the study must meet all of the following criteria:

1. Age ≥ 18 years
2. Histologically confirmed CD30-positive lymphoma with cutaneous presentation
3. Failure or intolerance to at least one prior therapy for the current disease
4. Presence of one or more cutaneous lesions (measuring at least 1 cm x 1 cm in size; if only one lesion is present it should be up to the investigator discretion to determine eligibility)
5. Eastern Cooperative Oncology Group (ECOG) performance status ≤ 2
6. Adequate organ and marrow function
 - a. Platelets $\geq 50,000/\mu\text{L}$
 - b. Absolute neutrophil count $\geq 1,000/\mu\text{L}$
 - c. Bilirubin $< 1.5 \times$ institutional upper limit of normal (ULN) or $< 3 \times$ ULN in patients with Gilbert's disease or liver involvement
 - d. Serum albumin $\geq 2.0 \text{ g/dL}$
 - e. Aspartate aminotransferase (AST)/Alanine aminotransferase (ALT) $\leq 2.5 \times$ institutional ULN or, in the case of liver involvement by the primary disease AST/ALT $\leq 5 \times$ ULN
 - f. Creatinine $\leq 1.5 \times$ institutional ULN or estimated creatinine clearance of $\geq 45 \text{ mL/min}$ by the Cockcroft-Gault equation or measured creatinine clearance $> 45 \text{ mL/min}$
7. Females of child bearing potential must have a negative serum pregnancy test with 7 days prior to first dose of treatment. Female patients of childbearing potential and all male partners must agree to use double barrier methods of contraception throughout the study period and for at least 30 days following investigational product discontinuation.

8. Ability to understand and the willingness to sign a written informed consent document.

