14.9 Pregnancy

AFM13 might cause harm when administered to a pregnant woman. There are no adequate and well-controlled studies in pregnant women.

Women of childbearing potential will be advised to avoid becoming pregnant while receiving treatment. Women enrolled in this study should either be post-menopausal, free from menses for >2 years, surgically sterilized, or willing to use 2 adequate barrier methods of contraception to prevent pregnancy or agree to abstain from heterosexual activity throughout the study, starting with Visit 1. Women of childbearing potential must have a negative serum pregnancy test (β -hCG) within 7 days prior to receiving the first dose of study drug. Men enrolled in the study must also agree to an adequate method of contraception for the duration of the study.

If a patient or their partner inadvertently becomes pregnant while on study, the patient will immediately be removed from the study and the drugs will be discontinued. Investigators will follow the patient monthly and document the patient’s status until the pregnancy has been completed or terminated. The outcome of the pregnancy will be reported to appropriate parties

within 24 hours if the outcome is an SAE (i.e. death, abortion, congenital anomaly, or other disabling or life-threatening complication to the mother or newborn). If a male patient's partner becomes pregnant on study, the pregnancy will be reported to appropriate parties. Reporting of pregnancy will follow the guidelines outlined in Section 14.3.

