14.13 Laboratory Assessments

Blood and urine samples will be collected for the following analyses:

- Complete Blood Count
- Serum Chemistry
- Urinalysis

A serum pregnancy test will be done on all women of childbearing potential; a negative test result must be obtained prior to the first administration of study treatment.

Samples will be collected per institutional procedures and analyzed in the local laboratory.

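### The only scheduled pregnancy test is at screening, so cycle 2 can start on a test up to 84 days old, although the first dose requires one no more than 7 days old

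*Combined protocol and SAP*

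**What the plan says.** Every place that mentions the pregnancy test ties it to the start of treatment:

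- Section 9.5, Table 2, has a single mark in the screening column. Footnote b reads: "Pregnancy test done at screening must be within 7 days of treatment initiation".
- Section 9.6.2, screening list: "Perform a pregnancy test on women of childbearing potential; negative results must be confirmed within 7 days prior to administration of first treatment".
- Section 10.11.1, criterion 7: "Females of child bearing potential must have a negative serum pregnancy test with 7 days prior to first dose of treatment".
- Section 14.13: "a negative test result must be obtained prior to the first administration of study treatment".
- Section 14.9 repeats the 7-day limit for a serum test before the first dose.

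The visit lists in 10.3 to 10.7 (Weeks 1 to 8, Week 11, restaging, End of Study) contain no further test. The optional second-cycle table in 9.5 repeats physical examination, ECG, vital signs, chemistry, hematology and coagulation, but has no pregnancy row.

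On risk, 14.9 states: "AFM13 might cause harm when administered to a pregnant woman". If a patient or a partner becomes pregnant on study, "the patient will immediately be removed from the study and the drugs will be discontinued".

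On exposure, 9.1 says: "The patient will receive one 8-week cycle of protocol treatment followed by 3 weeks off". Patients with at least stable disease then start a second cycle in Week 12. The synopsis caps treatment at two cycles.

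**The concern.** For the first dose, the plan treats a test more than 7 days old as too old. At the start of cycle 2 it sets no limit and gives no reason for the difference. Yet cycle 2 is a separate decision to re-expose the patient, taken after restaging and a 3-week break, at a visit where blood is drawn anyway.

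Section 14.9 contains a rule that must act at once when pregnancy occurs. After the first dose, no scheduled measurement can bring that rule into play. If the schedule is followed exactly, a woman with an early pregnancy that nobody suspects could enter cycle 2 and receive up to eight more weekly doses. What is at stake is patient safety. No endpoint, estimate or analysis set is affected.

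**Working it through.** The check is calendar arithmetic, taking Day 1 as the first dose.

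**Inputs**
- Earliest permitted test: 7 days before Day 1 (9.5 footnote b, 9.6.2, 10.11.1, 14.9). Latest: Day 1 itself, before the infusion.
- Cycle: 8 weekly doses, then 3 weeks off (9.1, Table 1).
- Cycle 2 start: Week 12 (9.1). Maximum: two cycles (synopsis).
- Longest permitted delay for an adverse event: 21 days (12.6, Table 5; 12.8).

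**The plan's own figure.** 8 + 3 = 11 weeks, so the next dosing week is Week 12, as stated. Week 12 Day 1 = 11 × 7 + 1 = Day 78.

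**Last doses.** Cycle 1: 7 × 7 + 1 = Day 50. Cycle 2: 78 + 7 × 7 = Day 127, which is Week 19 Day 1. First to last dose is 127 − 1 = 126 days (18 weeks), with 16 dosing weeks and a 3-week gap. In Cohort 3, Day 127 is the start of the last dosing week, because the continuous infusion then runs for 5 days.

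**Age of the test at the first cycle 2 dose.** (78 − 1) + 7 = 84 days if tested at the earliest permitted time, and 77 days if tested on Day 1. At most this is 84 / 7 = 12 times the limit set for the first dose.

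**Age of the test at the last dose.** (127 − 1) + 7 = 133 days at the earliest permitted test, and 126 days if tested on Day 1.

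**With one maximum delay (illustration).** First to last dose becomes 126 + 21 = 147 days (21 weeks), and the test can be 133 + 21 = 154 days old at the last dose.

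**Can existing blood draws serve?** Week 11 Day 1 = 10 × 7 + 1 = Day 71, and 78 − 71 = 7 days, so a sample on the nominal day just meets the limit. Visits have a window of 3 days either way and restaging one of 2 weeks, so a Week 11 sample may turn out too old. Chemistry and hematology are also drawn before the first cycle 2 infusion, which gives a second opportunity.

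**Period wording.** Criterion 7 in 10.11.1 requires contraception through the study and "for at least 30 days following investigational product discontinuation", which nominally runs to 127 + 30 = Day 157. Section 14.9 refers only to the duration of the study. Where the End of Study visit falls is itself unclear. Section 10.7 allows cycle 2 Week 11, which is 78 + 70 = Day 148, or 9 days before Day 157. Sections 10.1 and 10.8 point to 4 weeks after the last dose, which is 127 + 28 = Day 155, or 2 days before.

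**The case against.** The strongest reply is that test frequency after baseline is a design choice and that the documents state no standard requiring repeats. Women of childbearing potential must use double barrier contraception, patients are seen with adverse event review in every treatment week, and Table 2 allows additional assessments when clinically indicated. This largely stands. It limits the point to the start of cycle 2, where the plan's own 7-day limit provides the yardstick. It does not remove the point, because permission to test is not a requirement, and 14.9 itself expects that pregnancy may occur despite contraception.

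A reader might infer more than the documents support:

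- *That detection rests on the patient recognising her own pregnancy.* Clinical suspicion at a weekly visit can also prompt a test. What is missing is a scheduled repeat.
- *That pregnancies after End of Study go unreported.* Section 14.6 separately obliges the principal investigator to report any pregnancy associated with use of study drug, without limiting this to the time on study. Phone follow-up continues for up to a year (10.8).
- *That 14.9 shortens the contraception period.* Every enrolled woman of childbearing potential must meet criterion 7, so its 30 days bind whatever 14.9 says.
- *That tests are also needed mid-cycle and at End of Study.* Nothing in the documents points to those times.
- *That 133 days is the length of treatment.* It counts from the earliest permitted test. First to last dose is 126 days.

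Reach is also small. Section 9.1 describes Cohorts 1 to 3 as already given a preliminary analysis, so an amendment would mainly reach the 3 patients of Cohort 4 and the 3 of the expansion.

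**Conclusion.** The point holds, as a minor one. No pregnancy test is scheduled after screening, and the second cycle can begin on a test 77 to 84 days old. At the last weekly dose that test is 126 to 133 days old, on the nominal calendar without delays. This sits poorly beside the 7-day limit for the first dose and the warning and removal rule in 14.9.

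The result assumes that the visit lists and both schedule tables are complete as they stand, and that unscheduled tests are not routinely ordered. The number of women of childbearing potential is not given, so the number affected cannot be stated; about 6 patients (3 + 3) remain to be enrolled. A test would not help with a partner's pregnancy, which can become known only by report.

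The difference in period wording between 14.9 and 10.11.1 is a matter of drafting. It is not a gap in reporting.

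**What to change.** Reconcile Table 2 and footnote b with 14.9. Add a pregnancy-test row to the second-cycle schedule for women of childbearing potential, using blood already drawn at Week 11 or before the first cycle 2 dose, and apply the 7-day limit that the plan already sets for the first dose. Footnote b, 10.5 and 14.13 should carry the same wording. If the sample is taken on the first day of cycle 2, the result has to be available before the infusion. Dose, dosing schedule and the removal rule stay as they are.

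Separately, reconcile the period wording of 14.9 with the 30 days in 10.11.1 and the reporting duty in 14.6, so that one period is stated. In the same edit, correct the cross-reference for pregnancy reporting: 14.9 points to 14.3, which only defines a suspected unexpected serious adverse reaction.

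The cost is a few extra assays on existing samples, an occasional false positive that needs a repeat, and a short amendment.
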